6.2.1.1 Adverse Event Intensity

The Adverse Event Intensity refers to the extent to which an AE affects the subject's daily activities. Severity will be categorized according to the following criteria:

Mild:	The AE does not interfere with the subject's routine activities.
Moderate:	The AE interferes with the subject's daily routine, but usual routine activities can still be carried out.
Severe:	The AE results in the inability to perform routine activities.

The term "severity" is used to describe the intensity of an event. This is not the same as "serious". Seriousness, not severity, serves as the guide for defining regulatory reporting obligations. The highest severity grade attained should be reported, for AEs with divergent severities.

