6.2.1 Adverse Events

Patients will be instructed to report to the Investigator any AE that they experience. Investigators will ask about the occurrence of AEs at each visit. Investigators are required to document all AEs occurring during the clinical study, commencing with the signing of the informed consent form (ICF) through the End of Study Visit (scheduled at 42 days post last IB1001 dose). Adverse event recording will continue for patients who discontinue study treatment but remain on-study, until their ET Visit has been completed.

Adverse events will be recorded on designated eCRF pages. Each AE is to be characterized (i.e., verbatim term) and information provided regarding its seriousness, start and stop dates, intensity, outcome, and causal relationship with the study drug.

An AE is any undesirable physical, psychological or behavioral effect experienced by a patient during participation in an investigational study, in conjunction with the use of the drug or biologic, whether or not product-related. This includes any untoward signs or symptoms experienced by the patient from the time of signing of the informed consent until completion of the study.

Adverse events may include, but are not limited to:

- Subjective or objective symptoms spontaneously offered by the patient and/or observed by the Investigator or medical staff
- · Findings at physical examinations
- Laboratory abnormalities of clinical significance

Disease signs, symptoms, and/or laboratory abnormalities already existing prior to the use of the investigational product are not considered AEs after treatment unless they reoccur after the patient has recovered from the preexisting condition or, in the opinion of the Investigator, they represent a clinically significant exacerbation in intensity or frequency. Clinical significance is defined as any variation in signs, symptoms, or testing that has medical relevance and may result in an alteration in medical care. The Investigator will continue to monitor the patient until the assessment returns to Baseline or until the Investigator determines that follow-up is no longer medically necessary.

An AE does not include:

- Medical or surgical procedures (e.g., surgery, endoscopy, tooth extraction, transfusion); the
 condition that leads to the procedure is an adverse event; Planned surgical measures
 permitted by the clinical study protocol and the condition(s) leading to these measures are

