 not adverse events, if the condition(s) was (were) known before the start of study treatment.
 In the latter case, the condition should be reported as part of the subject's medical history.
- Pre-existing diseases or conditions present or detected prior to the start of study drug administration that do not worsen;
- Situations where an untoward medical event has not occurred (e.g., hospitalization for elective surgery, social and/or convenience admissions).

It is important that Investigators record accurate AE terms on eCRFs. Wherever possible, a specific disease or syndrome rather than individual associated signs and symptoms will be identified by the Investigator and recorded on the eCRF. However, if an observed or reported

sign or symptom is not considered a component of a specific disease or syndrome by the Investigator, or is atypical, it should be recorded as a separate AE on the eCRF.

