6.4.1 Adverse Events

See Section 6.2.1 of the Parent Study.

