5.7 Safety and tolerability evaluation

5.7.1 Adverse events

A treatment emergent adverse event (TEAE) is defined as an adverse event (AE) that appears during or after study treatment and was absent before.

An AE overview table will be created displaying the number and percentage of subjects experiencing a treatment-emergent adverse event (TEAE) and the number of TEAEs for: any TEAE, any mild/moderate/severe TEAE, any related/unrelated TEAE, any serious AE, and any TEAE leading to study discontinuation.

Furthermore, all TEAEs will be tabulated by System Organ Class (SOC) and Preferred Terms (PTs) within each SOC according to the MedDRA terminology list, using frequency counts (number of subjects with at least one event, and number of events) and percentage of subjects with the event.

TEAEs will also be tabulated by severity (mild/moderate/severe) and by relationship to study medication (related/unrelated). Similar tables will be created for TEAEs leading to premature discontinuation, SAEs and deaths, if applicable. These summary tables will be presented by decreasing frequency of occurrence based on SOC and PT.

In addition, similar TEAE tables (overall, by severity and by relationship, premature discontinuation, SAEs, and deaths) by SOC and PT will be presented per treatment cycle, and frequencies and percentages will be determined for the active treatment cycle and the washout cycle. The treatment cycle is the period between start of first treatment at Visit 2 and 24 hours after last dose at Visit 4. The washout cycle starts 24 hours after last dose at Visit 4 until and including Visit 6.

The summary tables will be accompanied by individual subject listings of *all* AEs including information on AE number, actual AE description, date/time of start and end of AE (or ongoing), PT (MedDRA), SOC (MedDRA), severity, relationship, pre-dose (yes/no), seriousness, action taken, outcome and other information collected in the CRF for adverse events. Pre-dose AEs are not considered to be treatment-emergent, except in case of worsening during/after study treatment (to be collected as separate AE in the database). AEs

starting prior to administration of the study drug will only be listed. In this listing, a clear distinction will be made between prior and treatment emergent events.

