For the full Extension Phase, the measurement at Visit 7 is considered the baseline. In case of missing Visit 7A data for safety measurements (e.g. for safety lab), and Visit 7B has occurred within 1 (+6) days of Visit 6, the Visit 6 data from the Parent Study should be used instead (data are not being re-entered in the database): see also Section [2.2.2](#) for clarification. No screen failures will be present in the data.

No screen failures will be present in the data.

For the full Extension Phase, a treatment emergent adverse event (TEAE) is defined as an adverse event (AE) that appears during or after the start of study treatment in the Extension Phase at Visit 7B and was absent before. As a consequence, AEs occurring during the washout phase between Visit 9 and Visit 10 will also be considered treatment emergent.

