6.3 Missing data

Data from withdrawal patients will be included in the analysis until their last assessment.

For handling missing data in the Extension Phase, similar approaches as described in Section [5.3](#) will be followed, with the alteration that “first dose date” is the first dosing of the Extension Phase. For AE and concomitant medication this indicates that events started during the Parent Study and continuing during the Extension Phase will be considered prior for the Extension Phase.

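### A worsening of an open AE counts as treatment-emergent only if entered as a separate record, which the protocol does not generally tell sites to create

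*Protocol*

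**What the plan says.** **Protocol.** Section 6.2.1 collects adverse events "commencing with the signing of the informed consent form (ICF) through the End of Study Visit", so events that begin before first dose are in the database. Each event is recorded with its seriousness, start and stop dates, intensity, outcome and causality. Section 6.2.1.1 holds the only rule for changing intensity: "The highest severity grade attained should be reported, for AEs with divergent severities". For signs, symptoms or laboratory abnormalities that existed before use of the drug, Section 6.2.1 makes an AE after treatment of those that recur after recovery or where, in the investigator's opinion, "they represent a clinically significant exacerbation in intensity or frequency". The same section removes from the AE definition "Pre-existing diseases or conditions present or detected prior to the start of study drug administration that do not worsen". For the Extension Phase, Appendix 6 Section 6.4.1 says only "See Section 6.2.1 of the Parent Study". Appendix 6 Section 6.4.6 adds that a worsened pre-existing condition found at physical examination is to be recorded as an AE.

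**SAP.** Sections 5.1 and 5.7.1 define a TEAE as an event that appears during or after treatment and was not there before. Section 5.3 sets the flag by comparing dates with first dose. Section 5.7.1 puts events that start before dosing in listings only, "except in case of worsening during/after study treatment (to be collected as separate AE in the database". For the Extension Phase, Section 6.1 requires that the event "appears during or after the start of study treatment in the Extension Phase at Visit 7B and was absent before". Section 6.3 adds that "events started during the Parent Study and continuing during the Extension Phase will be considered prior for the Extension Phase". Section 6.7 says that the Extension safety evaluation is similar to Section 5.7.

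**The concern.** The SAP means worsening to count, but makes that depend on a data-entry practice that the protocol does not set out. Reporting one highest grade for an event of varying severity reads most naturally as one entry, which keeps its original start date. A flag set from dates then cannot see that the event became worse on drug.

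Worsening of an existing event under treatment is a basic safety signal. Safety and tolerability are a secondary objective of the Parent Study, and long-term safety and tolerability are one of the Extension Phase. If sites differ in how they enter worsening, the same clinical course would be a TEAE at one site and a listing line at another.

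**Working it through.** The documents give no figure to reproduce here. The check applies the SAP's rules to records that the protocol's wording allows.

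| Case | Course of the event | How entered | Result under the SAP |
|---|---|---|---|
| 1 | Mild after consent, before first Parent dose; severe on drug | One record, highest grade | Pre-dose start date: listed only, in no TEAE table |
| 2 | As case 1 | New record at worsening | Start date after first dose: counted as a TEAE |
| 3 | Begins on drug in the Parent Study, continues, worsens after Visit 7B | One record, highest grade | Prior for the Extension: absent from Extension TEAE tables, present in Parent TEAE tables |
| 4 | As case 3 | New record at worsening | Start date after Visit 7B: counted as an Extension TEAE |
| 5 | Begins before first Parent dose, continues, worsens in the Extension | One record, highest grade | Absent from both sets of TEAE tables |

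The loss is complete in cases 1 and 5, confined to the Extension tables in case 3, and nil in cases 2 and 4. The data-entry choice alone separates case 1 from case 2, and case 3 from case 4.

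**Grade shown in case 3.** SAP 5.4 analyses the Parent Study and writes an interim report once Visit 6 is complete, and SAP 9 splits the Parent data from the Extension data. A grade raised during later dosing can post-date that report. The Parent tables may therefore show the event at its earlier grade while the Extension tables omit it.

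**Does the exacerbation clause close the gap?** The clause in Protocol 6.2.1 concerns findings that existed before the investigational product was used. It can reach cases 1 and 5. It does not clearly reach case 3, where the event began on drug. It also makes an exacerbation an AE without saying that an event already open needs a new record and a new onset date.

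**Size.** Inputs: 20 Extension patients, the number used in Protocol Appendix 6 Section 8.10 and SAP 2.4.2. Two rates are assumptions, not document figures: 10% to 30% of patients have an event open at Visit 7B, and 10% to 25% of those worsen on drug.

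Affected patients = patients × proportion with an open event × proportion worsening

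- Low: 20 × 0.10 × 0.10 = 0.2
- High: 20 × 0.30 × 0.25 = 1.5

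Both assume that every such worsening is kept as one record.

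**What one case does.** Moving one patient out of the severe-TEAE row changes 1/20 (5%) to 0/20. As an illustration only, since the SAP plans frequencies and not these limits, the exact (Clopper-Pearson) one-sided 95% upper limits are:

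- 0/20: 1 − 0.05^(1/20) = 13.9%
- 1/20: the p that solves (1 − p)^20 + 20p(1 − p)^19 = 0.05, which is 21.6%

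**The case against.** The strongest reply is that nothing in Protocol 6.2.1.1 says one record. It states which grade to report, not when a record opens or closes, and it does not forbid a new entry. The SAP's parenthesis can be read as a collection rule in its own right. Protocol 9.1 leaves data capture and entry to a data management plan that is not among these documents, so sites may have had the instruction. Protocol 6.2.1 and Appendix 6 Section 6.4.6 treat a clinically significant exacerbation, or a worsened condition found at examination, as an AE. SAP 6.7 carries the worsening exception of Section 5.7 into the Extension.

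Much of this stands. Single-record entry is an inference, and the loss depends on site practice. It does not remove the point: the carried-over exception still requires the separate record, SAP 6.3 states none of its own, and case 3 is not clearly covered.

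A reader might infer more than the documents support:

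- **That worsened events disappear from the report.** They do not. SAP 5.7.1 lists all AEs, SAEs and deaths have their own listings, and Parent events that began on drug are in the Parent TEAE tables.
- **That serious events are under-counted.** This is weakly supported. The overview row in SAP 5.7.1 is for any serious AE, not serious TEAEs.
- **That the severity-by-cycle tables hide drug-period severity.** An event mild on drug and severe in washout would be tabulated as severe in the treatment cycle, which is the opposite direction.
- **That the size scales to the 39 patients to be enrolled.** The assumed rates refer to Visit 7B, and the Extension is planned around 20.

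**Conclusion.** The protocol and the SAP do not fit together on worsening adverse events. Under single-record entry, the stated rules keep an on-drug worsening out of the TEAE tables altogether if the event was open at the first Parent dose. They keep it out of the Extension TEAE tables if the event began on drug in the Parent Study and worsened after Visit 7B.

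This is a risk that depends on how sites enter worsening, not a demonstrated loss. On the assumed rates it affects about 0.2 to 1.5 of 20 Extension patients, and fewer if some sites already open new records. The number is small, but so is the denominator, and one case can decide whether a row of the severity table is empty. The correction is worth making because it carries out what the SAP already intends.

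**What to change.** Reconcile the passages as follows.

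1. **Protocol 6.2.1.1** (which also serves the Extension through Appendix 6 Section 6.4.1): add a data-entry rule. An AE open at the first Parent dose, or at the first Extension dose at Visit 7B, that then worsens in intensity or becomes serious is entered as a new AE dated at the worsening. Otherwise the highest-grade rule applies unchanged.
2. **SAP 5.1, 5.7.1 and 6.1:** define a TEAE as an event absent before the first dose of the phase, or present before it and worsened after it.
3. **SAP 6.3:** except worsened events from the class of prior events.
4. **Data already entered:** identify events open at either first dose and obtain the worsening date by site query against source. The audit trail in Protocol 9.1 records when a data field was changed, not when the patient became worse, so it cannot supply onset dates.

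The cost is one sentence in the AE instructions, matching SAP wording and a limited query round. TEAE counts may rise slightly.

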6.2.1.2 Adverse Event Relatedness

The Principal Investigator (Investigator) will make a judgment regarding whether or not, in his/her opinion, the AE was related to study drug. However, even if the Investigator feels there is no relationship to the study drug, the AE MUST be recorded on the adverse event eCRF. Below are guidelines for relationship assessment:

Causality of Adverse Event:

The Causality of Adverse Events refers to the relationship of the AE to study drug. Causality will be categorized according to the following criteria:

Not related:	Adverse events for which a reasonable explanation for an alternative cause is considered plausible, e.g., no study drug taken, plausible clinical alternative like accidental injury, expected progression of underlying or concomitant disease, pharmacologically incompatible temporal relationship, or intercurrent illness.
Related:	Adverse events for which a reasonably possible clinical and/or pharmacological relationship to study drug cannot be excluded, e.g., lacking plausible alternatives.

6.2.2 Serious Adverse Events

Serious adverse events will be reportable from the time the patient signs the ICF through their last study visit (e.g. Visit 6 or Visit 12) or until the Investigator in collaboration with IntraBio Ltd determines that follow-up is no longer necessary. Serious adverse events that are suspected to be drug related will be reported even if they occur up to 30 days after the patient has taken the last dose of study drug. If a related SAE is ongoing at the end of the study or when a patient

withdraws from the study, appropriate safety follow-up, including additional laboratory tests as required, will continue for 30 days.

An SAE is any AE that results in any of the following outcomes:

- Death
- Life-threatening experience
- Inpatient hospitalization or prolongation of existing hospitalization
- Persistent or significant disability/incapacity
- Congenital anomaly or Birth Defect
- Important medical events that, based upon appropriate medical judgment, may
 jeopardize the patient and may require medical or surgical intervention to prevent
 one of the outcomes listed above.

Life-threatening experience. Any adverse experience that places the patient, in the view of the reporter, at immediate risk of death from the adverse experience as it occurred, i.e., does not include an adverse experience that had it occurred in a more severe form, might have caused death.

Required or prolonged inpatient hospitalization. The adverse experience resulted in an initial inpatient hospitalization or prolonged an existing hospitalization of the patient. If a patient is hospitalized as part of the clinical use of the product, a period of normal hospitalization will be outlined in the protocol or by the judgment of the Investigator. Hospitalizations longer than this period will be prolonged hospitalizations.

Persistent or significant disability/incapacity. An adverse experience that resulted in a substantial disruption of a person's ability to conduct normal life functions.

Congenital Anomaly. The exposure of the patient to the drug or biologic during pregnancy that is judged to have resulted in the congenital anomaly/birth defect.

Important medical events. Adverse experiences that may not result in death, be life-threatening, or require hospitalization may be considered a serious adverse experience when, based upon appropriate medical judgment, may jeopardize the patient or subject and may require medical or surgical intervention to prevent 1 of the outcomes listed above. Important medical events or interventions may be considered an SAE based upon medical judgment of the Investigator.

6.2.2.1 Reporting Serious Adverse Events

SAEs will be reported promptly once the Investigator determines that the event meets the protocol definition of an SAE. The Investigator or designate will fill out the SAE reporting form in the eCRF within 24 hours of his/her becoming aware of these events. In addition, for fatal and life-threatening events, the Sponsor's Medical Monitor should be contacted immediately. Contact numbers for the Medical Monitor (including after-hours cover) will be provided to the site before any patients are screened and upon receipt should be kept in the Site's study binder.

The SAE Reporting Form of the eCRF will always be completed as thoroughly as possible with all available details of the event within the designated time frames. The Investigator will always

CONFIDENTIAL Version 7.0, 10 Oct 2022 Page 50 of 161

provide an assessment of causality at the time of the initial report as described in Section 6.2.1.2.

If the Investigator does not have all information regarding an SAE, he/she will not wait to receive additional information before completing the form. The SAE reporting form will be updated when additional information is received within 24 hours of receipt of such information.

The completion of the SAE Reporting Form in the eCRF is the preferred method for Reporting SAEs. Only if a technical failure prevents the ability to report an SAE in the eCRF, then the paper SAE Reporting Form provided by the Sponsor must be completed and

The fax and or email instructions can be found on the paper SAE Reporting Forms, which are filed in the Investigator Site File.

6.2.2.2 Responsibilities of the Sponsor

The Sponsor or their delegate, is responsible for fulfilling all obligations regarding notification of Regulatory Authorities, Independent Ethics Committees (IECs)/ Institutional Review Board (IRBs), and investigators according to applicable regulatory requirements (expedited and periodic reporting, e.g., serious unexpected suspected adverse reactions, Development Safety Update Report).

6.2.3 Pregnancy

Every effort should be made to prevent pregnancy during the study treatment period. All patients of reproductive potential involved in the study are required to use highly effective methods of contraception during the study and for 28 days after the last IB1001 dose. Female patients will be instructed to notify the Investigator immediately if they discover they are pregnant. Pregnancy data during the study will be reported using the SAE reporting process (see Section 6.2.2). Since it will be necessary to collect detailed information on the course of any pregnancy occurring in a patient on study the Investigator will be provided with the pregnancy notification forms and specific guidance for completing these forms once the initial AE form documenting a pregnancy is received within 24 hours.

Pregnant patients will discontinue study medication for the duration of the pregnancy. The pregnancy will be followed by the Investigator and the outcome of the pregnancy will be reported to the Pharmacovigilance group.

At Visit 2, Visit 4, Visit 6, and then Early Termination Visit (if applicable), females of childbearing potential will have a urine dipstick pregnancy test (analyzed on site).

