4.1 Inclusion Criteria

Individuals who meet all of the following criteria are eligible to participate in the study:

- Written informed consent signed by the patient and/or their legal representative/ parent/ impartial witness
- 2. Male or female aged ≥6 years in Europe OR ≥18 years in the United States with a confirmed diagnosis of NPC at the time of signing informed consent. Confirmed diagnosis includes [Patterson et al, 2017]:
 - a) Clinical features and positive biomarker screen and/or filipin test without genetic tests results (has not been performed)
 - b) Clinical features and positive genetic test
 - c) Clinical features and positive biomarker screen and/or filipin test but only one NPC mutation identified on genetic test
 - d) Clinical features with positive biomarker screen and/or filipin test and positive genetic test
- 3. Females of childbearing potential, defined as a premenopausal female capable of becoming pregnant, will be included if they are either sexually inactive (sexually abstinent⁶ for 14 days prior to the first dose and confirm to continue through 28 days after the last dose) or using one of the following highly effective contraceptives (i.e. results in <1% failure rate when used consistently and correctly) 14 days prior to the first dose continuing through 28 days after the last dose:
 - a) intrauterine device (IUD);
 - b) surgical sterilization of the partner (vasectomy for 6 months minimum);
 - c) combined (estrogen or progestogen containing) hormonal contraception associated with the inhibition of ovulation (either oral, intravaginal, or transdermal);
 - d) progestogen only hormonal contraception associated with the inhibition of ovulation (either oral, injectable, or implantable);
 - e) intrauterine hormone releasing system (IUS);
 - f) bilateral tubal occlusion.
- 4. Females of non-childbearing potential must have undergone one of the following sterilization procedures at least 6 months prior to the first dose:

Periodic abstinence (calendar, symptothermal, post-ovulation methods), withdrawal (coitus interruptus), spermicides only, and lactational amenorrhoea method (LAM) are not acceptable methods of contraception. As well, female condom and male condom should not be used together.

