⁶ Sexual abstinence is considered a highly effective method only if defined as refraining from heterosexual intercourse during the entire period of risk associated with the study treatments. In this trial abstinence is only acceptable if in line with the patient's preferred and usual lifestyle.

- a) hysteroscopic sterilization;
- b) bilateral tubal ligation or bilateral salpingectomy;
- c) hysterectomy;
- d) bilateral oophorectomy;
- **OR** be postmenopausal with amenorrhea for at least 1 year prior to the first dose and follicle stimulating hormone (FSH) serum levels consistent with postmenopausal status. FSH analysis for postmenopausal women will be done at screening. FSH levels should be in the postmenopausal range as determined by the central laboratory.
- 5. Non-vasectomized male patient agrees to use a condom with spermicide or abstain from sexual intercourse during the study until 90 days beyond the last dose of study medication and the female partner agrees to comply with inclusion criteria 3 or 4. For a vasectomized male who has had his vasectomy 6 months or more prior to study start, it is required that they use a condom during sexual intercourse. A male who has been vasectomized less than 6 months prior to study start must follow the same restrictions as a non-vasectomized male.
- 6. If male, patient agrees not to donate sperm from the first dose until 90 days after their last dose.
- 7. Patients must fall within:
 - a) A SARA score of $5 \le X \le 33$ points (out of 40)

AND

- b) Either:
 - i. Within the 2-7 range (0-8 range) of the Gait subtest of the SARA scale

OR

- ii. Be able to perform the 9-Hole Peg Test with Dominant Hand (9HPT-D) (SCAFI subtest) in $20 \le X \le 150$ seconds.
- 8. Weight ≥15 kg at screening.
- 9. Patients are willing to disclose their existing medications/therapies for (the symptoms) of NPC, including those on the prohibited medication list. Non-prohibited medications/therapies (e.g. miglustat, concomitant speech therapy, and physiotherapy) are permitted provided:
 - a) The Investigator does not believe the medication/therapy will interfere with the study protocol/results
 - b) Patients have been on a stable dose/duration and type of therapy for at least 42 days before **Visit 1** (Baseline 1)
 - c) Patients are willing to maintain a stable dose/do not change their therapy throughout the duration of the study.

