4.1 Inclusion Criteria

- 1. Completed Visit 6 of the IB1001-201 Parent Study
- The Principal Investigator determines further treatment with IB1001 to be in patient's best interest
- Written informed consent signed by the patient and/or their legal representative/parent/ impartial witness for participation in the Extension Phase
- 4. Patients are willing to continue to remain without the following prohibited medication from **Visit 6** throughout the duration the Extension Phase:
 - a) Aminopyridines (including sustained-release form);
 - b) N-Acetyl-DL-Leucine (e.g. Tanganil®);
 - N-Acetyl-L-Leucine (prohibited if not provided as investigational medicinal product [IMP]);
 - d) Riluzole;
 - e) Gabapentin;
 - f) Varenicline;
 - g) Chlorzoxazone;
 - h) Sulfasalazine;
 - i) Rosuvastatin.

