6.4.3 Pregnancy

The policies for pregnancy are identical to the Parent Study (see Section 6.2.3 of the Parent Study) except that at all visits of the Extension Phase (Visits 7 through Visit 10 and the Extension Phase Early Termination Visit [if applicable]), females of childbearing potential will have a urine dipstick pregnancy test (analyzed on site).

CONFIDENTIAL Version 7.0, 10 Oct 2022

⁴⁶ In addition, the same investigator should perform the SARA assessment at all extension phase Visits (Visit 7 – Visit 12)

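### Section 6.2.3 gives every patient of reproductive potential a 28-day post-dose contraception period, but inclusion criterion 5 requires 90 days for non-vasectomized and recently vasectomized males

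*Protocol*

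**What the plan says.** Protocol Section 6.2.3 (Pregnancy) opens with a general rule: "All patients of reproductive potential involved in the study are required to use highly effective methods of contraception". With its duration, the requirement is that these patients are "required to use highly effective methods of contraception during the study and for 28 days after the last IB1001 dose". The next sentence is limited to one sex: "Female patients will be instructed to notify the Investigator immediately if they discover they are pregnant". The section gives no separate male period and does not refer to the inclusion criteria.

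Section 4.1 sets the periods by sex:

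- **Criterion 3**, females of childbearing potential: contraception runs "14 days prior to the first dose continuing through 28 days after the last dose".
- **Criterion 5**, non-vasectomized males: use a condom with spermicide or "abstain from sexual intercourse during the study until 90 days beyond the last dose of study medication". The synopsis repeats this.
- **Criterion 5**, recent vasectomy: "A male who has been vasectomized less than 6 months prior to study start must follow the same restrictions as a non-vasectomized male".
- **Criterion 6**, all males: no sperm donation until 90 days after the last dose.

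For the Extension Phase, Appendix 6 Section 6.4.3 says: "The policies for pregnancy are identical to the Parent Study (see Section 6.2.3 of the Parent Study"), with a change only to the pregnancy test schedule. The Extension Phase inclusion criteria begin with "Completed Visit 6 of the IB1001-201 Parent Study" and contain no contraception rule for either sex.

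**The concern.** The 28 days in 6.2.3 matches the female period exactly, yet the sentence applies it to all patients of reproductive potential. For two groups of males the same protocol sets a period more than three times as long. Criterion 5 is applied when a patient enters the study, whereas 6.2.3 and Extension 6.4.3 are the sections staff would consult on pregnancy during conduct. A site using only those sections could tell a male patient to stop precautions too early.

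This is a reproductive safety instruction, so the period should not depend on which section is opened. It matters most where no study visit follows the last dose by much: after Visit 12, and after early termination when the patient does not complete the remaining visits. The consent form text is not in the copy reviewed, so what patients are actually told cannot be judged.

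**Working it through.** **Inputs**

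| Item | Value | Source |
|---|---|---|
| Post-dose period, all patients of reproductive potential | 28 days | Protocol 6.2.3 |
| Post-dose period, females of childbearing potential | 28 days | Protocol 4.1, criterion 3 |
| Post-dose period, non-vasectomized or recently vasectomized males | 90 days | Protocol 4.1, criterion 5; synopsis |
| Visit 6 after last dose | 42 days, +7 | Protocol 3.1.2.3 and 6.2.1 |
| COVID-19 postponement of Visit 6 | allowed, no upper limit | Protocol 3.1.2.5.2 |
| Early termination visit | preferably 7–14 days after last dose | Protocol 4.3 |
| After Visit 12 | no further visit; no washout cycle | Appendix 6, 3.1.2.4 and 3.3; SAP 6.7 |

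**Step 1: whose period is 28 days?** It equals the criterion 3 figure and no male figure. Both male post-dose periods, for contraception (criterion 5) and sperm donation (criterion 6), are 90 days. So 6.2.3 states the female period for both sexes.

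**Step 2: the difference at face value.** 90 − 28 = 62 days.

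**Step 3: allow for time on study after the last dose.** Section 6.2.3 also requires contraception during the study. If the patient's last visit is D days after the last dose, reliance on 6.2.3 alone gives cover to the later of day 28 and day D:

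shortfall = max(0, 90 − max(28, D))

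- Visit 6 on day 42, no rollover: 90 − 42 = 48 days.
- Visit 6 on day 49, the end of its window, no rollover: 90 − 49 = 41 days.
- Visit 6 postponed to day 90 or later: 0 days. This needs a delay of at least 90 − 49 = 41 days beyond the window.
- Early termination visit on day 7–14 and no later visit: the 28 days governs, so 90 − 28 = 62 days. This is a maximum, because Section 4.3 asks patients who stop drug to complete the remaining visits as far as possible.
- Dosing to Visit 12 with nothing after it: 90 − 28 = 62 days.

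The interval between Visit 6 and Visit 7 cannot be quantified in the same way, because SAP 2.2.2 allows the transition to take weeks or months.

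**Step 4: the Extension Phase.** Criterion 5 runs to the last dose of study medication, with no restriction to the Parent Study. Appendix 6 Section 3.3 counts the study as both parts. Criterion 5 can therefore be read as running from the last Extension Phase dose, and nothing cancels it. But the section on pregnancy in Appendix 6 cites only 6.2.3, and no Extension Phase text gives a male period in days.

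**Outside the comparison.** Males vasectomized 6 months or more before study start must use a condom, but criterion 5 gives no post-dose period for them.

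**The case against.** The best defence is that the two texts can be reconciled. Highly effective contraception is defined in criterion 3, with a list of methods that does not include condom with spermicide. Criterion 5 also asks that a male patient's female partner comply with criterion 3 or 4. On that reading, 28 days of highly effective contraception applies to female patients and to male patients' partners, while the 90 days is a separate male duty that 6.2.3 leaves alone. This does not fit the sentence. Its subject is patients, not partners, and the section says female patients when it means only females. If the sentence was meant for females only, its wording is still wrong and males are left with no instruction in that section.

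Second, 6.2.3 does not release males from criterion 5, and a man who follows 90 days satisfies both rules. Criterion 5 is explicit, repeated in the synopsis, and part of the eligibility check. This stands as a limit on the likely harm: a site would have to overlook a criterion it had already applied. It does not make 28 days the correct figure for males.

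Third, Appendix 6 Section 1.1 says that partners of women of childbearing potential continue to be held to strict precautions in the Extension Phase. That supports reading criterion 5 as still in force. It gives no number of days, so the period remains unclear. The absence of a male rule from the Extension Phase criteria is weak evidence alone, since those criteria restate no contraception rule at all.

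Finally, SAP 6.7 defines adverse event reporting cycles, not contraception. That is true, but the visit schedule itself ends at Visit 12, the last visit of the second treatment period.

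**Conclusion.** The inconsistency is real. Section 6.2.3 states a period that is correct for females of childbearing potential and too short for the two male groups covered by criterion 5. The difference is 62 days at worst, 41 to 48 days with Visit 6 in its window and no rollover, and zero if Visit 6 is at day 90 or later.

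These figures rest on two assumptions: that a site relies on 6.2.3 alone, directly or through Extension 6.4.3, and that time on study ends at the patient's own last visit. Nothing in the documents shows that any site or patient was misled. The protocol gives no rationale for the 90 days, so the clinical consequence of a shortfall cannot be assessed here. No endpoint, procedure or analysis is affected. It should be corrected because it is a safety instruction and the correction is nearly free.

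**What to change.** - **Protocol 6.2.3:** limit the 28 days to females of childbearing potential, state 90 days after the last dose for the males covered by criterion 5, and refer to inclusion criteria 3 to 6, which also brings in the sperm donation rule.
- **Appendix 6, Section 6.4.3:** state that these periods run from the last Extension Phase dose.
- **Consent form:** check that its text gives the same periods.

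The cost is one sentence in each section and one document check. Visits, procedures and analyses stay as they are.
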